10.6. Appendix 6: Kidney Safety: Monitoring Guidelines

10.6.1. Laboratory Assessment of Change in Kidney Function and Detection of Kidney Injury

Standard kidney safety monitoring requires assessment of baseline and postbaseline Screat measurement to estimate kidney function [Screat-based eGFR] or creatinine clearance [eCrCl]). Obtaining Screening or Baseline Scys and postbaseline reflex Scys (if confirmed Screat increase ≥ 0.3 mg/dL) makes it feasible to distinguish AKI from DICI. If Screat increase is confirmed after baseline, then reflex measurement of Scys is indicated:

ADULTS: Currently, 2021 CKD-EPI eGFR equations (Screat only-based and combined Screat plus Scys-based) are valid for use in adults only. At baseline Screat and Scys values are needed to calculate 2021 CKD-EPI eGFR by Screat only-based equation (see Table 10.7.2.1.) and by combined Screat plus Scys-based equation. When post-baseline Screat increase ≥ 0.3 mg/dL is confirmed, then reflex Scys measurement is needed to enable post-baseline comparison of eGFR changes (Screat only-based eGFR and combined Screat plus Scys eGFR).

10.6.2. Age-Specific Kidney Function Calculation Recommendations

10.6.2.1. Adults (18 Years and Above)—2021 CKD-EPI Equations

eGFR (mL/min/1.73m²)¹¹

2021 CKD-EPI Screat Only	Screat (mg/dL)	Scys (mg/L)	Recommended eGFR Equation
Female	if ≤ 0.7	NA	$eGFR = 143 \times (\text{Screat}/0.7)^{-0.241} \times (0.9938)^{\text{Age}}$
Female	if > 0.7	NA	$eGFR = 143 \times (\text{Screat}/0.7)^{-1.200} \times (0.9938)^{\text{Age}}$
Male	if ≤ 0.9	NA	$eGFR = 142 \times (\text{Screat}/0.9)^{-0.302} \times (0.9938)^{\text{Age}}$
Male	if > 0.9	NA	$eGFR = 142 \times (\text{Screat}/0.9)^{-1.200} \times (0.9938)^{\text{Age}}$
2021 CKD-EPI Screat-Scys Combined	Screat (mg/dL)	Scys (mg/L)	Recommended eGFR Equation
Female	if ≤ 0.7	if ≤ 0.8	$eGFR = 130 \times (\text{Screat}/0.7)^{-0.219} \times (\text{Scys}/0.8)^{-0.323} \times (0.9961)^{\text{Age}}$
Female	if ≤ 0.7	if > 0.8	$eGFR = 130 \times (\text{Screat}/0.7)^{-0.219} \times (\text{Scys}/0.8)^{-0.778} \times (0.9961)^{\text{Age}}$
Female	if > 0.7	if ≤ 0.8	$eGFR = 130 \times (\text{Screat}/0.7)^{-0.544} \times (\text{Scys}/0.8)^{-0.323} \times (0.9961)^{\text{Age}}$
Female	if > 0.7	if > 0.8	$eGFR = 130 \times (\text{Screat}/0.7)^{-0.544} \times (\text{Scys}/0.8)^{-0.778} \times (0.9961)^{\text{Age}}$
Male	if ≤ 0.9	if ≤ 0.8	$eGFR = 135 \times (\text{Screat}/0.9)^{-0.144} \times (\text{Scys}/0.8)^{-0.323} \times (0.9961)^{\text{Age}}$
Male	if ≤ 0.9	if > 0.8	$eGFR = 135 \times (\text{Screat}/0.9)^{-0.144} \times (\text{Scys}/0.8)^{-0.778} \times (0.9961)^{\text{Age}}$
Male	if > 0.9	if ≤ 0.8	$eGFR = 135 \times (\text{Screat}/0.9)^{-0.544} \times (\text{Scys}/0.8)^{-0.323} \times (0.9961)^{\text{Age}}$
Male	if > 0.9	if > 0.8	$eGFR = 135 \times (\text{Screat}/0.9)^{-0.544} \times (\text{Scys}/0.8)^{-0.778} \times (0.9961)^{\text{Age}}$

10.6.3. Kidney Function Calculation Tools

The sponsor has provided the following resources to investigational sites when required to calculate age-specific kidney function at Screening, Baseline, and post-Baseline visits. Site calculations of kidney function can be performed manually, using the age appropriate

formulae (see [Section 10.6.2](#)) and can use recommended online kidney function calculators to reduce the likelihood of a calculation error.

The United States National Kidney Foundation Online Calculators.

- Adults (18 years and above) - 2021 CKD-EPI Creatinine Online Calculator (eGFR):

Investigational sites are responsible to ensure that the accurate age-specific equation is selected and that the correct units for serum creatinine (mg/dL only), serum cystatin C (mg/L only), total body weight (kg only), and age (years). Investigators are expected to (i) review and confirm correctness of the kidney function calculation results and (ii) evaluate the calculated value within the context of historical information available to them in the participant's medical record. Investigators are responsible for the clinical oversight of the participant eligibility process, kidney function calculation, and dose selection and adjustments per study protocol. Investigators are encouraged to direct questions or uncertainties regarding kidney function and dosing to the Pfizer Clinical Team and Medical Monitor, if needed.

10.6.4. Adverse Event Grading for Kidney Safety Laboratory Abnormalities

AE grading for decline in kidney function (ie, eGFR or eCrCl) will be according to Kidney Disease: Improving Global Outcomes (KDIGO) criteria for both pediatric and adult participants.

KDIGO criteria grade (G)	Study Population	G1	G2	G3	G4	G5
Decreased Kidney Function due to either Acute or Chronic Kidney Injury	Adult participants eGFR (mL/min/1.73m ²)	≥90	≥60 to 89	30 to 59	15 to 29	<15

KDIGO albuminuria (A) criteria	A1	A2	A3
Albumin-to-creatinine ratio (ACR)	<30 mg/g OR <3 mg/mmol	30 to 300 mg/g OR 3 to 30 mg/mmol	>300 mg/g OR >30 mg/mmol

10.7. Appendix 7: ECG Findings of Potential Clinical Concern

ECG Findings That May Qualify as AEs

Marked sinus bradycardia (rate <40 bpm) lasting minutes.New PR interval prolongation >280 ms.New prolongation of QTcF to >480 ms (absolute).New prolongation of QTcF by >60 ms from baseline.New-onset atrial flutter or fibrillation, with controlled ventricular response rate: ie, rate <120 bpm.New-onset type I second-degree (Wenckebach) AV block of >30-second duration.Frequent PVCs, triplets, or short intervals (<30 seconds) of consecutive ventricular complexes.
ECG Findings That May Qualify as SAEs

QTcF prolongation >500 ms.Absolute value of QTcF > 450 ms AND QTcF change from baseline >60 ms.New ST-T changes suggestive of myocardial ischemia.New-onset LBBB (QRS complex >120 ms).New-onset right bundle branch block (QRS complex >120 ms).Symptomatic bradycardia.Asystole
In awake, symptom-free participants in sinus rhythm, with documented asystolic pauses ≥ 3 seconds or any escape rate <40 bpm, or with an escape rhythm that is below the AV node;In awake, symptom-free participants with atrial fibrillation and bradycardia with 1 or more asystolic pauses of at least 5 seconds or longer.Atrial flutter or fibrillation, with rapid ventricular response rate: rapid = rate >120 bpm.

- Sustained supraventricular tachycardia (rate >120 bpm) (“sustained” = short duration with relevant symptoms or lasting >1 minute).
- Ventricular rhythms >30 seconds’ duration, including idioventricular rhythm (HR <40 bpm), accelerated idioventricular rhythm (HR >40 bpm to <100 bpm), and monomorphic/polymorphic ventricular tachycardia (HR >100 bpm [such as torsades de pointes]).
- Type II second-degree (Mobitz II) AV block.
- Complete (third-degree) heart block.

ECG Findings That Qualify as SAEs

- Change in pattern suggestive of new myocardial infarction.
- Sustained ventricular tachyarrhythmias (>30-seconds duration).
- Second- or third-degree AV block requiring pacemaker placement.
- Asystolic pauses requiring pacemaker placement.
- Atrial flutter or fibrillation with rapid ventricular response requiring cardioversion.
- Ventricular fibrillation/flutter.
- At the discretion of the investigator, any arrhythmia classified as an adverse experience.

The major events of potential clinical concern listed above are recommended as “alerts” or notifications from the core ECG laboratory to the investigator and Pfizer study team, and not to be considered as all-inclusive of what is to be reported as AEs/SAEs.

10.8. Appendix 8: Prohibited Concomitant Medications That May Result in DDI

The prohibited concomitant medications listed below should not be taken with sisunatovir for the period of time at least equal to the required washout period listed in the table, and throughout the conduct of the study.

The Pfizer study team is to be notified of any prohibited medications taken during the study. After consulting with the sponsor, the investigator will make a judgment on the ongoing participation of any participant with prohibited medication use during the study.

This list of drugs prohibited for potential DDI concerns with the IMP may be revised during the course of the study with written notification from sponsor, to include or exclude specific drugs or drug categories for various reasons (eg, emerging DDI results for the IMP, availability of new information in literature on the DDI potential of other drugs), if the overall benefit: risk assessment is not impacted or if the changes do not significantly impact the safety of participants or the scientific value of the trial

Strong and moderate CYP3A4 and P-gp inhibitors or inducers are prohibited, as these medications may have meaningful impact on the pharmacokinetics of sisunatovir.

Sisunatovir is a CYP3A4 inhibitor and therefore sensitive and narrow therapeutic index CYP3A4 substrates are also prohibited in this study.

Sisunatovir also may be an inhibitor of OCT1 and MATE1 transporters; therefore, sensitive substrates of these transporters are excluded.

This is not an all-inclusive list. Site staff should consult with the sponsor or designee with any questions regarding potential DDI.

Prohibited Concomitant Medications

CYP3A Inhibitors		CYP3A Inducers	
Moderate	Strong	Moderate	Strong
Aprepitant	Boceprevir	Bosentan	Apalutamide
Ciprofloxacin	Cobicistat	Efavirenz	Carbamazepine
Conivaptan	Danoprevir	Etravirine	Enzalutamide
Crizotinib	Dasabuvir	Phenobarbital	Mitotane
Cyclosporine	Elvitegravir	Primidone	Phenytoin
Diltiazem	Indinavir		Rifampin
Dronedarone	Itraconazole		St. John's wort
Erythromycin	Ketoconazole		
Fluconazole	Lopinavir		
Fluvoxamine	Paritaprevir		
Imatinib	Ombitasvir		
Tofisopam	Posaconazole		
Verapamil	Ritonavir		
	Saquinavir		
	Telaprevir		
	Tipranavir		
	Telithromycin		
	Troleandomycin		
	Voriconazole		

PFIZER CONFIDENTIAL

CT02-GSOP Clinical Pharmacology Protocol Template (14 April 2023)

Page 86

Sensitive CYP3A Substrates		CYP3A Substrates with Narrow Therapeutic Index
Alfentanil	Lovastatin	Alfentanil
Atorvastatin	Lurasidone	Astemizole
Avanafil	Maraviroc	Cisapride
Budesonide	Midazolam	Cyclosporine
Buspirone	Naloxegol	Dihydroergotamine
Darifenacin	Nisoldipine	Ergotamine
Darunavir	Quetiapine	Fentanyl
Dasatinib	Sildenafil	Pimozone
Dronedarone	Simvastatin	Quinidine
Ebastine	Siroliimus	Siroliimus
Eletriptan	Tacrolimus	Tacrolimus
Eplerenone	Ticagrelor	Terfenadine
Everolimus	Tolvaptan	
Ibrutinib	Tipranavir	
Indinavir	Triazolam	
Felodipine	Vardenafil	
Lomitapide		
Sensitive MATE1 Substrates		
Metformin		
P-gp Inhibitors		P-gp Inducers
Atazanavir	Lopinavir	Apalutamide
Boceprevir	Lumacaftor	Atazanavir
Cobicistat	Mifepristone	Fosamprenavir
Conivaptan	Nelfinavir	Lopinavir
Cyclosporine	Ombitasvir and Paritaprevir and Ritonavir and Dasabuvir	Rifampicin
Darunavir	Posaconazole	st. John's wort (Hypericum perforatum) extract
Diltiazem	Ritonavir	Tipranavir
Elvitegravir and Cobicistat and Emtricitabine and Tenofovir DF	Saquinavir	Verapamil
Erythromycin	Telaprevir	
Glecaprevir and Pibrentasvir	Tipranavir	
Indinavir	Tucatinib	
Itraconazole	Verapamil	
Ketoconazole	Vonoprazan and Amoxicillin and Clarithromycin	
Lonafarnib	Voxilaprevir	
Sensitive OCT Substrates		
Imatinib		

Not an all-inclusive list.

Investigators should consult the product label for any other medication used during the study for information regarding medication that is prohibited for concomitant use.

10.9. Appendix 9: Abbreviations

The following is a list of abbreviations that may be used in the protocol.

Abbreviation	Term
A1 to A3	albuminuria (KDIGO albuminuria severity standardization)
Abs	absolute
ADL	activity/activities of daily living
AE	adverse event
AKI	acute kidney injury
ALP	alkaline phosphatase
ALT	alanine aminotransferase
AST	aspartate aminotransferase
AUC	area under the curve
AUC ₁₂	area under the concentration-time curve from time zero to 12 hours
AUC ₂₄	area under the concentration-time curve from time zero to 24 hours (1 day)
AUC _{inf}	area under the concentration-time curve from time 0 to infinity
AUC _{last}	area under the concentration-time curve from time 0 to the time of last quantifiable concentration
AUC _{tau}	area under the concentration-time profile from time zero to time tau (the dosing interval), where tau = 12 hours for BID dosing
AV	atrioventricular
AxMP	auxiliary medicinal product
BID	twice-daily dosing
BMI	body mass index
BP	blood pressure
bpm	beats per minute
BUN	blood urea nitrogen
C _{av}	average concentration at steady state
CFR	Code of Federal Regulations
CI	confidence interval
CIOMS	Council for International Organizations of Medical Sciences
CK	creatine kinase
CKD-EPI	chronic kidney disease epidemiology
CL/F	apparent clearance
C _{max}	maximum observed plasma concentration
CO ₂	carbon dioxide (bicarbonate)
COVID-19	coronavirus disease 2019
CRF	case report form
CRO	contract research organization
CRU	clinical research unit
CSR	Clinical Study Report
CT	clinical trial
CTIS	Clinical Trial Information System

Abbreviation	Term
C _{trough}	lowest concentration observed during the dosing interval
CV	Cardiovascular/coefficient of variation
CYP	cytochrome P450
DCT	data collection tool
DDI	drug-drug interaction
DIC	drug in capsule
DILI	drug-induced liver injury
DPB	sisunatovir dry powder blend
EC	ethics committee
ECC	emergency contact card
ECG	electrocardiogram or electrocardiography
eCrCl	estimated creatinine clearance
eCRF	electronic case report form
EDB	exposure during breastfeeding
E-DMC	External Data Monitoring Committee
EDP	exposure during pregnancy
EGFR	epidermal growth factor receptor
eSAE	electronic serious adverse event
ET	early termination
EU	European Union
EudraCT	European Union Drug Regulating Authorities Clinical Trials (European Clinical Trials Database)
FDA	Food and Drug Administration
FIH	first in human
FSH	follicle-stimulating hormone
F/U	follow-up
GCP	Good Clinical Practice
GFR	glomerular filtration rate
GGT	gamma-glutamyl transferase
GI	gastrointestinal
HBcAb	hepatitis B core antibody
HbsAb	hepatitis B surface antibody
HbsAg	hepatitis B surface antigen
HBP cyclodextrin	hydroxypropyl- β -cyclodextrin
HCVAb	hepatitis C antibody
HIV	human immunodeficiency virus
HR	heart rate
HRT	hormone replacement therapy
IB	Investigator's Brochure
IBC	isobutyl carnitine
ICD	informed consent document
ICH	International Council for Harmonisation of Technical Requirements for Pharmaceuticals for Human Use

Abbreviation	Term
ICU	intensive care unit
ID	identification
IMP	investigational medicinal product
IND	Investigational New Drug
INR	international normalized ratio
IPAL	Investigational Product Accountability Log
IPM	investigational product manual
IRB	Institutional Review Board
IV	intravenous(ly)
K	Proportionality constant for Bedside and Modified Schwartz Equations (kidney function)
KDIGO	Kidney Disease Improving Global Outcomes
LBBB	left bundle branch block
LFT	liver function test
LRTI	lower respiratory tract infection
MAD	multiple ascending dose
MATE	multidrug and toxin extrusion
MQI	medically qualified individual
MRT	mean residence time
MTD	maximum tolerated dose
NA	not applicable/not available
NIMP	noninvestigational medicinal product
NMN	N1-METHYLNICOTINAMIDE
NOAEL	no-observed-adverse-effect level
OAT	organic anion transporting
OATP	organic anion transporting polypeptide
OCT	organic cation transporter
PD	pharmacodynamic(s)
PE	physical examination
P-gp	p-glycoprotein
PI	principal investigator
PIMS	Phase One Management System
PK	pharmacokinetic(s)
PR	pulse rate
PSSA	Pfizer's Serious Adverse Event Submission Assistant
PT	prothrombin time
PTR	peak-trough ratio
PVC	premature ventricular contraction/complex
Q12	every 12
QTc	corrected QT interval
QTcF	QTc corrected using Fridericia's formula
qual	qualitative
R _{ac}	observed accumulation ratio for AUC

Abbreviation	Term
R _{ac,Cmax}	observed accumulation ratio for C _{max}
RBC	red blood cell
RSV	respiratory syncytial virus
SAD	single ascending dose
SADE	serious adverse device effect
SAE	serious adverse event
SAP	Statistical Analysis Plan
SARS-CoV-2	severe acute respiratory syndrome coronavirus 2
Scr	serum creatinine
Scys	serum cystatin C
SD	single dose
SoA	schedule of activities
SOC	system organ class
SOP	standard operating procedure
SRSD	Single Reference Safety Document
SUSAR	Suspected Unexpected Serious Adverse Reaction
t _{1/2}	terminal elimination half-life
TB	tuberculosis
T bili	total bilirubin
TEAE	treatment emergent adverse event
THC	tetrahydrocannabinol
T _{max}	time to reach C _{max}
UACR	urine albumin/creatinine ratio
ULN	upper limit of normal
US	United States
V _z /F	apparent volume of distribution
WBC	white blood cell
WOCBP	woman/women of childbearing potential

1. VERSION HISTORY

Table 1. Summary of Changes

Version/ Date	Associated Protocol Amendment	Rationale	Specific Changes
1 08 Aug 2023	Original 9 Jun 2023	N/A	N/A

2. INTRODUCTION

PF-07923568 (sisunatovir, formerly RV521) is being developed to act as a highly potent, selective, orally available agent to treat RSV infection. Sisunatovir is an inhibitor of RSV fusion (F) protein mediated fusion that is currently being investigated for the treatment of RSV infection.

The purpose of the study is to evaluate the PK, safety and tolerability of sisunatovir (PF-07923568) in Chinese healthy adult participants. This information is being collected to support further clinical development as well as drug registration in China.

This statistical analysis plan (SAP) provides the detailed methodology for summary and statistical analyses of the data collected in Study C5241018.

2.1. Modifications to the Analysis Plan Described in the Protocol

None.

2.2. Study Objectives, Endpoints, and Estimands

The following are the objectives and endpoints in this study. Estimand framework will not be applied to this Phase 1 study in healthy participants.

Table 2. Study Objectives and Endpoints

Type	Objectives	Endpoints
	Primary:	
Pharmacokinetics	
 To evaluate the PK of sisunatovir after single dose and multiple doses in Chinese healthy participants 	Sisunatovir plasma exposure for single and multiple doses: 
 Post dose on Day 1: C_{max}, AUC_{last}, AUC_{tau} ($\tau_{1/2}=12$), and AUC_{inf} as data permit. Post first dose on Day 4: C_{max}, AUC_{tau} Post dose on Day 8: C_{max}, AUC_{tau}
	Secondary:	
Pharmacokinetics	
 To further characterize the PK profile of sisunatovir after single dose and multiple doses of sisunatovir in Chinese healthy participants 	Additional sisunatovir plasma PK parameters: 
 Post dose on Day 1: T_{max}, $t_{1/2}$, MRT, V_z/F, and CL/F as data permit Post first dose on Day 4: T_{max} Post dose on Day 8: T_{max}, $t_{1/2}$, accumulation ratio on AUC_{tau} (R_{ac}) and on C_{max} ($R_{ac, Cmax}$), MRT, V_z/F, CL/F, C_{trough}, C_{av}, AUC_{last}, AUC_{inf} and PTR as data permit
Safety	
 To evaluate the safety and tolerability of sisunatovir following single and multiple dose in Chinese healthy participants 	
 AEs/SAEs, clinical safety laboratory tests, vital signs, 12-lead ECGs
Tertiary/Exploratory:		Tertiary/Exploratory:
CCI		
Pharmacokinetics	
 To explore PK of sisunatovir by microsampling technique, if feasible 	
 Concentration of sisunatovir from paired samples obtained via microsampling compared to plasma sampling (if possible)

2.3. Study Design

This is a Phase 1, single-center, open-label and single-arm study to investigate PK, safety and tolerability of 200 mg sisunatovir given as a single dose on Day 1 in a fasted state followed by repeated twice daily doses (200 mg BID, Q12 hours) from Days 4-7 plus 1 morning dose on Day 8 in a fed state in Chinese healthy participants. Approximately 12 participants in total will be included in this study. If a participant discontinues before completing the study, or withdraws for reasons unrelated to the safety of the treatment, the participant may be replaced at the discretion of the investigator upon consultation with the sponsor.

The study will consist of a Screening visit, a Treatment period of single dosing (Day -1 to Day 3) and multiple dosing (Day 4 to Day 11), and a Follow-up contact. The total duration

of participation from the Screening visit to the Follow-up contact will be up to approximately 71 days.

3. ENDPOINTS AND BASELINE VARIABLES: DEFINITIONS AND CONVENTIONS

3.1. Primary Endpoint(s)

As listed in [Section 2.2](#), the primary endpoints are related to Sisunatovir plasma exposure after single and multiple doses, and are detailed in Table 3.

3.2. Secondary Endpoint(s)

The secondary endpoints are additional pharmacokinetics parameters after single and multiple doses of Sisunatovir as detailed in Table 3, as well as safety endpoints described in [Section 3.5](#).

Table 3. Sisunatovir Plasma PK Parameter Definitions

Parameter	Study Day	Definition	Method of Determination
C_{max}	1, 4, 8	Maximum observed concentration	Observed directly from data
T_{max}	1, 4, 8	Time to reach maximum concentration	Observed directly from data
AUC_{inf}^a	1, 8	Area under the concentration-time curve from time 0 to infinity	$AUC_{last} + (C_{last}/k_{el})$, where C_{last} is the predicted plasma concentration at the last quantifiable time point estimated from the log-linear regression analysis
AUC_{last}	1, 8	Area under the concentration-time curve from time 0 to the time of last quantifiable concentration	Linear/Log trapezoidal method
AUC_{tau}	1, 4, 8	Area under the concentration time curve from time 0 to the time of the end of the dosing interval (τ), where $\tau=12$ hours	Linear/Log trapezoidal method.
$t_{1/2}^a$	1, 8	Terminal half-life	$\log_e(2)/k_{el}$, where k_{el} is the terminal phase rate constant calculated by a linear regression of the log-linear concentration-time curve
MRT^a	1, 8	Mean residence time	Day 1: $MRT = AUMC_{inf}/AUC_{inf}$ Day 8: $[AUMC_{tau} + \tau(AUC_{inf} - AUC_{tau})]/AUC_{tau}$ where $AUMC_{inf}$ is the area under the first moment curve from zero time to infinity $AUMC_{tau}$ is area under the first moment curve over the dosing interval τ .

Table 3. Sisunatovir Plasma PK Parameter Definitions

Parameter	Study Day	Definition	Method of Determination
V_z/F^a	1	Apparent volume of distribution	$Dose/(AUC_{inf} \times k_{el})$
CL/F^a	1, 8	Apparent oral clearance	$Dose/AUC_{inf}$
R_{ac}^a	8	Accumulation ratio on AUC_{tau}	$AUC_{12}(\text{Day 8})/AUC_{12}(\text{Day 4})$
$R_{ac,C_{max}}^a$	8	Accumulation ratio on C_{max}	$C_{max}(\text{Day 8})/C_{max}(\text{Day 4})$
C_{trough}	6, 7, 8	Lowest concentration observed during the dosing interval	Observed directly from data
C_{av}	8	Average concentration at steady state	$AUC_{12}(\text{Day 8})/12 \text{ hours.}$
V_z/F^a	8	Apparent volume of distribution at steady state	$V_z/F = Dose/(AUC_{tau} \times k_{el})$
PTR	8	Peak-trough ratio	C_{max}/C_{trough}

a. If data permit.

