Pharmacokinetic blood sampling			X	X	X	X		X	X	X	X	X	X		X	
 • All screening should be done \leq28 days before the first dose. • Day relative to start of study intervention (Day 1). • Follow-up may occur via telephone contact and must occur 28 to 35 days after administration of the last dose of study intervention.
CRU discharge														X		
Serious and nonserious AE monitoring	X	→	→	→		→	→	→	→	→	→	→	→	→	→	

Table 2. Pharmacokinetic Sampling Times

Visit Identifier	On-Treatment Period													Notes	
Study Day	Day 1, Day 4 and Day 8														
Hours Before/After Dose	0	1	2	3	4	5	6	8	10	12	14	24	48	72	Hour 0 = predose sample collection
Study intervention administration	X									X					• Dosing at 12 hours only on Day 4
PK blood sampling on Day 1 and Day 8	X	X	X	X	X	X	X	X	X	X	X	X	X	X	
PK blood sampling on Day 4	X*	X	X	X	X	X	X	X	X						
 PK sample at 0 hour on Day 4 is the same sample at 72 hours post dose on Day 1. PK sample at 12 hours post-dose must be collected prior to dosing;
PK microsampling (Tasso®) (if feasible)			X		X		X	X		X					
 Time-matched to PK blood sampling. To be collected on Day 4 only.
Blood/Plasma ratio sampling (if feasible)					X		X			X					
 Whole blood to be aliquoted from PK blood samples on Day 4 only.

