9.3. Appendix 3: List of Abbreviations

Abbreviation	Term
AE	adverse event
AUC	area under the curve
BLQ	below the limit of quantitation
BP	blood pressure
C_{av}	average concentration
CI	confidence interval
C_{max}	maximum observed concentration
CL/F	apparent clearance
CRF	case report form
C_{trough}	pre-dose concentration
CV	coefficient of variation
ECG	electrocardiogram
LLQ	lower limit of quantitation
MRT	mean residence time
NC	not calculated
ND	not done
NS	No sample
PK	pharmacokinetic(s)
PR	Pulse rate
PT	preferred term
PTR	peak-trough ratio
QTc	corrected QT
QTcF	corrected QT (Fridericia method)
R_{ac}	accumulation ratio for AUC_{tau}
$R_{ac,C_{max}}$	accumulation ratio for C_{max}
SAE	serious adverse event
SAP	statistical analysis plan
SD	standard deviation
SoA	schedule of activities
SOC	System organ class
TEAE	Treatment-emergent adverse event
V_z/F	apparent volume of distribution

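### C_trough has two definitions, and as tabulated it compares a Day 8 minimum of ten samples with what appear to be single samples on Days 6 and 7

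*SAP*

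**What the plan says.** SAP Table 3 (Section 3.2) assigns C_trough to Days 6, 7 and 8 and defines it as "Lowest concentration observed during the dosing interval", read directly from the data. Protocol Table 4 (Section 9.3.1.2) has the same entry, and the protocol abbreviation list (Appendix 9) repeats it: "lowest concentration observed during the dosing interval". SAP Appendix 3 alone differs and gives "pre-dose concentration". SAP Section 2.1 declares no change from the protocol's analysis, so this is not a declared modification.

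The endpoint lists in protocol Section 3 and SAP Section 2.2 name the parameter only under Day 8, in the run "C_{trough}, C_{av}, AUC_{last}, AUC_{inf} and PTR as data permit". PTR ("Peak-trough ratio") is C_max divided by C_trough on Day 8. SAP Section 6.1 and Table 4 summarise C_trough by study day under one label.

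On sampling, protocol Table 2 is headed "Day 1, Day 4 and Day 8" and notes "Hour 0 = predose sample collection". Its row "PK blood sampling on Day 1 and Day 8" marks every time point, ten of them from 0 to 12 h. Days 6 and 7 are ticked for PK blood in Table 1, but Table 2 gives them no number and no clock time.

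**The concern.** A programmer working from Table 3 would take the lowest of ten Day 8 values. A programmer working from the SAP abbreviation list would take the 0 h value. The two can give different Day 8 troughs and different PTRs from the same data.

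Applying the tabulated rule consistently does not make the days comparable. With one sample, the minimum is simply that sample. With ten, it is the lowest of ten noisy readings, and it can also pick up a dip after dosing if absorption is delayed. In a by-day table, a series that is truly flat over Days 6, 7 and 8 may appear to drop on Day 8, and one still rising may appear flat. C_trough is the only PK parameter planned on successive multiple-dose days. Protocol Section 4.2 relies on steady state having been reached when it compares these data with earlier studies, so readers are likely to look at that series.

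**Working it through.** **Step 1: samples on Days 6 and 7.** Inputs are about 3 mL per draw (protocol Section 8.5), a PK total of about 115 mL (Section 8.1), and the Table 2 grid.

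- Day 1: 14 samples. Day 8: 14 samples.
- Day 4: the 0 h sample is the Day 1 72 h sample, so 1 to 10 h gives 8 new draws. The 12 h draw makes 9. Its cell reads as blank in the text available, but the table note requires it.
- With k draws on each of Days 6 and 7, volume = 3 × (14 + 8 or 9 + 14 + 2k) mL.

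| k | Draws | Volume (mL) |
|---|---|---|
| 0 | 36-37 | 108-111 |
| 1 | 38-39 | 114-117 |
| 2 | 40-41 | 120-123 |

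Microsampling adds at most 5 × 0.1 = 0.5 mL, and the blood/plasma aliquots come out of the PK draws. Among schedules with equal draws on the two days, only k = 1 reproduces about 115 mL. Unequal numbers (one draw and two) would give 3 × (14 + 8 + 14 + 3) = 117 mL only if the required Day 4 12 h draw were dropped; with that draw the total is 120 mL. One sample per day is therefore a sound inference, although it is not stated. Pre-dose timing on those days remains an assumption.

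**Step 2: direction.** The 0 h sample is one of the ten, so C_min ≤ C_predose for every participant. Hence PTR from the minimum ÷ PTR from pre-dose = C_predose / C_min ≥ 1.

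**Step 3: size under stated assumptions.** Half-life 7, 8.5 or 10 h and single-dose T_max 5 or 6 h reflect the ranges in protocol Section 2.2.4. The nine 12-hourly doses come from the design (4 × 2 + 1). Lag and residual CV are assumptions, because the documents give neither. The model is one-compartment with first-order absorption:

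- ke = ln 2 / half-life, and ka solves ln(ka/ke)/(ka − ke) = T_max − lag.
- C(t) = sum over i = 0 to 8 of ka/(ka − ke) × [exp(−ke·s) − exp(−ka·s)], with s = t + 12i − lag, counted only when s > 0.
- Log-normal residual error with SD = √ln(1 + CV²), sampled at 0, 1, 2, 3, 4, 5, 6, 8, 10 and 12 h, with 40,000 profiles per setting.

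The geometric mean of C_predose / C_min, as a range over half-life and T_max, is:

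| Residual CV | Lag 0-0.5 h | Lag 1 h |
|---|---|---|
| 0 (noise-free) | 1.00 | 1.07-1.10 |
| 5% | 1.03 | 1.08-1.11 |
| 10% | 1.06-1.07 | 1.12-1.14 |
| 20% | 1.15-1.19 | 1.23-1.24 |

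A hand check uses only the 0 h and 12 h samples, which are level at steady state. The lower of two equal-mean normal values lies on average 0.56 SD below the mean. At 10% CV, SD = √ln(1.01) = 0.0998 and exp(0.56 × 0.0998) = 1.06, which agrees with the no-lag entry.

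An example for PTR takes half-life 8.5 h, T_max 5 h, lag 1 h and no noise. Then ke = 0.0815 and ka = 0.566, and PTR is 1.64 from the pre-dose value and 1.78 from the minimum (ratio 1.08).

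**The case against.** Three of the four places that define C_trough agree, and the outlier is a single glossary line. Correcting that line would remove the contradiction. This is true, but it would leave one label covering a minimum of ten on Day 8 and a single reading on each of Days 6 and 7, so the comparability problem would stay.

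A reader might infer that PTR is inflated. The documents do not support that. C_max over the interval minimum is a coherent ratio and is what both tables specify. It is higher only relative to a pre-dose PTR, and the difference can be zero. What stands is that the number depends on which definition is programmed.

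A reader might also infer that the study loses its only check on steady state. It does not. SAP Section 6.2.1 lists every concentration and summarises them by study day and nominal time, so the Day 8 pre-dose value can be read there. No steady-state test is planned, and protocol Sections 2.2.4 and 4.2 rest steady state on earlier data. That concentration summary does, however, need a nominal time for the Day 6 and 7 samples, and Table 2 does not give one.

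Finally, the percentages come from assumed lag and noise in a linear model, whereas protocol Section 2.2.4 reports 2-4 fold accumulation and greater than dose-proportional exposure. This objection stands in full: the direction is certain and the size is not.

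**Conclusion.** The point holds, and it is minor. The definitions conflict. As tabulated, the by-day C_trough summary mixes two estimators, and the Day 8 value can only equal or fall below its own pre-dose value. That direction follows by construction. The claim of single samples on Days 6 and 7 rests on the 115 mL total at 3 mL per draw.

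The size cannot be determined from the documents. Under a residual CV of 5-20% and a lag of 0-1 h, both assumed, pre-dose/minimum is about 1.03-1.24. For a smooth profile with lag up to 0.5 h it is 1.00. The effect is confined to secondary, descriptive parameters. The primary C_max and AUC_tau, the accumulation ratios and the sample size do not use C_trough.

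**What to change.** 1. In SAP Table 3 and protocol Table 4, define C_trough on Days 6, 7 and 8 as the observed pre-dose (0 h) concentration, and make both abbreviation lists match.
2. Add C_min, Day 8 only, as the lowest observed concentration over 0-12 h, and include it in SAP Table 4.
3. State in the PTR row whether the denominator is C_trough or C_min.
4. In protocol Table 2, state the number and time of the Day 6 and Day 7 samples. If they are not pre-dose, step 1 does not work as written and the days cannot be compared under one label.
5. Align the endpoint lists, which name C_trough for Day 8 only, with the tables.

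The cost is wording and one extra derived parameter, with no extra samples. C_trough is not a primary endpoint, so under protocol Section 9 the SAP can carry the new definition, recorded in SAP Section 2.1, and the protocol text can follow at its next revision. It should be settled before database lock.
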